6.8 Procedures for Collecting Adverse Event Information

Before subsequent drug administration(s), subjects will be questioned concerning unusual symptoms that may have occurred since the previous administration of the study drug(s).

Any adverse events, whether serious or non-serious, will be monitored throughout the study and followed to resolution, when possible, regardless of whether the subject is still participating in the study. The investigator will remain on-call until the end of the study.

6.9 Procedures for Reporting Adverse Events

Subjects will be instructed to report any adverse events that may arise during the study to clinic personnel.

All symptoms will be recorded and will be reviewed by the investigator before any subsequent drug administration.

When appropriate, medical tests and examinations will be performed to document resolution of the event(s).

Adverse events will be classified according to the MedDRA (Medical Dictionary for Protocol Version: 00

Regulatory Activities) and reported by severity, duration, relationship to the study medication(s), and action taken.

All serious adverse events occurring during the study, whether considered to be related to the study drug, will be reported to Teva within 48 hours. SAE report(s) will be typed in English.

These SAE reports will contain the following information:

- A. Study name/number
- B. Study Drug
- C. Investigator details (name, phone, fax, e-mail)
- D. Subject Number
- E. Subject Initials
- F. Subject Demographics
- G. Clinical Event
 - 1) Description
 - 2) Date of onset
 - 3) Treatment (drug, dose, dosage form)
 - 4) Relationship to study drug
 - 5) Action taken regarding the study drug
- H. If the AE was Fatal
 - 1) Cause of death (whether the death was related to the study drug)
 - 2) Autopsy findings (if available).

The notification about any serious adverse event will be directed to the Sponsor.

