Short Title	Phase II ^b Efficacy and Safety Evaluation of TC Cream in Treating Patients with Psoriasis Vulgaris.																				
Protocol Number	105883-1																				
Clinical Trial Phase	Phase II ^b																				
IND Sponsor	Psoriasis Research Institute of Guangzhou, Guangdong, China																				
Study Centers	Multi-centers: (1) (2)																				
Primary Objective	To observe the efficacy and safety of TC Cream twice daily compared to placebo over 8 weeks in subjects of US population with stable psoriasis.																				
Secondary Objectives	To evaluate the effects and improvements of TC Cream on the quality of life in subjects with psoriasis vulgaris (stable stage) based on Psoriasis Disability Index (PDI) and Dermatology Life Quality Index (DLQI); and to determine whether there is further improvement or recurrence of psoriasis after the cessation of TC Cream after 8 weeks treatment of psoriasis vulgaris of stable stage.																				
Exploratory Objectives	To investigate and summarize the curative effects and recurrence rate of TC Cream on treated psoriasis patients of US population																				
Sample Size	Total: 88 Subjects (44 for the treatment group and 44 for the control group) 
  
 Clinical centers	Stable Stage	Total	
 
 Arm 1 TC	Arm 2 Vehicle	
   
 Center 1				
 
 Center 2				
 
 Total				
  
			Clinical centers	Stable Stage		Total	Arm 1 TC	Arm 2 Vehicle	Center 1				Center 2				Total			
Clinical centers	Stable Stage		Total																		
	Arm 1 TC	Arm 2 Vehicle																			
Center 1																					
Center 2																					
Total																					
Study Population	Male or female patients of 18-70 years old of any race with psoriasis vulgaris of stable stage																				
Duration of Administration	8 weeks																				
Washout	4 weeks for any topical or systemic corticosteroids, anti-inflammatories, antibiotics, 3-months for any systemic retinoids or biologics, or any investigational treatment																				

Protocol Version: 00

period	
Duration of Study	6 months

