3.5.2 Study Agents Supply

The sponsor (PRIG) will supply sufficient quantities of the study drugs to allow completion of this study. Study agents (test and control) are supplied in identical 25g collapsible tubes.

Designated clinical staff will be responsible for monitoring the receipt, storage, dispensing, and accounting for all study medications in accordance with Good Clinical Practice (GCP) and FDA regulations.

The appearance and packaging of the placebo will be consistent with those of the investigational product. The subjects and the investigators couldn't distinguish them. The product name, strength, the manufacturer's name, and lot/batch number will be identified on each container. The control agent will also include an expiry date. The study drugs will be placed under appropriate storage conditions in an area with controlled access.

Every subject will receive a packaging kit; exterior and interior packages should be kept with their respective labels.

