6.2 Adverse Event Definition and Classification

An adverse event (AE) is defined as any untoward medical occurrence in a patient or clinical investigation subject administered a pharmaceutical product that does not necessarily have a causal relationship with the treatment. An AE can, therefore, be any unfavorable and unintended sign (including abnormal laboratory finding), symptom, or disease temporarily associated with the use of a medicinal (investigational) product, whether related to the medicinal (investigational) product.

CTCAE term (AE description) and grade: The descriptions and grading scales found in the Common Terminology Criteria for Adverse Events (CTCAE) version 4.0 will be utilized for AE reporting. All appropriate treatment areas should have access to a copy of the CTCAE version 4.0.

A copy of the CTCAE version 4.0 can be downloaded from the CTEP website.

http://ctep.cancer.gov/protocolDevelopment/electronic_applications/cTC.htm.

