6.6 Severity of Adverse Events

Adverse events will be classified according to the following severity scale:

- Grade 1(Mild) - The adverse event is easily tolerated and does not interfere with daily activity.
- Grade 2 (Moderate) - The adverse event interferes with daily activity, but the subject

is still able to function.

- Grade 3 (Severe) - The adverse event is incapacitating and requires medical intervention.

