6.7 Relationship to Study Drug

Adverse events will be assessed for the relationship to the study drug (causality) according to the following scale:

Unrelated - The event is independent of the study drug.

Unlikely - The event may or may not follow a reasonable temporal sequence from drug administration and can plausibly be explained and/or attributed to something other than the study drug.

Possible - The event follows a reasonable temporal sequence from drug administration, follows a clinically reasonable response on withdrawal, and is unlikely to be attributed to something other than the study drug.

Probable - The event follows a reasonable temporal sequence from drug administration, follows a clinically reasonable response on withdrawal, and cannot be reasonably explained by something other than the study drug.

Definite - There is clear evidence to reveal causality, and other possible existing factors can be excluded. It follows a reasonable temporal sequence from the time of drug administration. It follows a known response pattern to the suspected drug. It disappears on cessation and recurs with reintroduction of the test drug.

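### Section 6.9 ties its only SAE deadline to a company with no stated role and gives the Sponsor none; AE severity has two unreconciled graded scales

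*Combined protocol and SAP*

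**What the plan says.** **SAE recipient.** Section 6.9 states that all SAEs, whether or not related to study drug, "will be reported to Teva within 48 hours". It then lists the contents of the report and ends: "The notification about any serious adverse event will be directed to the Sponsor". That last sentence carries no time limit. The synopsis gives the IND sponsor as "Psoriasis Research Institute of Guangzhou, Guangdong, China", and section 3.5.2 confirms it: "The sponsor (PRIG) will supply sufficient quantities of the study drugs". Sections 10.6 and 12 are consistent with this.

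**Severity.** Section 6.2 says that the descriptions and grading scales of the "Common Terminology Criteria for Adverse Events (CTCAE) version 4.0 will be utilized for AE reporting". Section 6.6 then classifies adverse events (AEs) on a scale of its own, built on interference with daily activity. Its top category is: "Grade 3 (Severe) - The adverse event is incapacitating and requires medical intervention". Section 7 refers to a CTCAE grade when it discusses withdrawal for infection.

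**Causality.** Section 6.7 gives one scale with five categories: *Unrelated*, *Unlikely*, *Possible*, *Probable* and *Definite*. An event is *Possible* only if, besides its timing and its response on withdrawal, it "is unlikely to be attributed to something other than the study drug".

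**Analysis.** Section 6.9 has AEs reported by severity and by relationship, among other attributes. Section 9.2.4.2 promises only descriptive statistics.

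**The concern.** Safety is part of the primary objective in the synopsis, so the rules for routing and classifying safety events carry real weight.

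The routing rule is operative: site staff will follow it when an SAE occurs. As written, the only clock runs to a party whose function is not explained, and the party holding the IND has no clock.

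The severity problem affects what can be tabulated. If some sites grade by CTCAE and others by section 6.6, an entry of Grade 2 does not have one meaning, and a severity table by arm would pool two measures.

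The causality wording affects how events are sorted. Section 6.1 lists erythema among the most frequent AEs seen with the cream, and erythema is also a scored sign of psoriasis in sections 5.1.1 and 5.1.2. The disease itself will therefore often be a plausible alternative cause, and the definitions need to handle that case cleanly.

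**Working it through.** No figure in the plan bears on this point, so there is nothing to recompute. The check sets the passages side by side.

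**1. SAE routing (section 6.9)**

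| | First statement | Closing statement |
|---|---|---|
| Recipient | Teva | the Sponsor |
| Time limit | 48 hours | none |
| Role given elsewhere in the supplied text | none | IND sponsor, PRIG (synopsis, 3.5.2, 10.6) |

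The supplied text contains one mention of Teva and several identifications of PRIG as sponsor. It contains one SAE deadline. The two sentences can be read in two ways:

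- *They describe one duty.* Then Teva and the Sponsor would have to be the same party, which the synopsis contradicts, or one would have to act for the other, which is not stated.
- *They describe two duties.* Then the 48 hours applies to Teva only, and notice to PRIG has no limit.

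On neither reading does the text give PRIG a clear deadline.

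**2. Severity (sections 6.2 and 6.6)**

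| | 6.2 | 6.6 |
|---|---|---|
| Scale | CTCAE 4.0 descriptions and grades | protocol's own, Grades 1 to 3 |
| Basis | CTCAE term | effect on daily activity; need for intervention at the top |
| Stated use | AE reporting | classification of AEs |

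Both scales use numbered grades, and no sentence says which governs or how one maps to the other. Section 6.3 lists fatal and life-threatening outcomes and section 6.9 has fields for a fatal event, but the section 6.6 scale has no grade beyond Severe. A death and a non-life-threatening incapacitating event would share Grade 3, or the death would go ungraded. Section 8.3 requires AEs to be graded and assessed for severity and causality without naming a scale. Section 9.2.4.2 does not say which scale is tabulated.

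**3. Causality (section 6.7)**

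| Category | Timing | Response on withdrawal | Alternative cause |
|---|---|---|---|
| *Unlikely* | reasonable or not | not mentioned | plausible |
| *Possible* | reasonable | required | improbable |
| *Probable* | reasonable | required | not a reasonable explanation |

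The first two criteria are identical for *Possible* and *Probable*, and the third differs only in shade. Now take an event with reasonable timing, resolution on withdrawal and a plausible second cause. It fails *Possible* on the third criterion and meets *Unlikely*, which accepts either timing. No category is left for an event that could as well be due to the drug as to something else.

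Two further features make the upper categories hard to use. *Possible* and *Probable* both need a response on withdrawal, which cannot be seen while a subject keeps applying the cream. *Definite* needs recurrence on reintroduction, which the plan does not describe.

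**The case against.** The strongest reply on routing is that a site which follows the whole of section 6.9 does notify the Sponsor. A reader might infer that SAE reports go only to an outside company. The documents do not support that, because the closing sentence names the Sponsor. What stands is that the recipients are unreconciled and the deadline belongs to the unexplained one. Title and contact pages were also removed from the text supplied, so a delegated safety role for Teva could have been stated there. For the same reason it cannot be assumed that the name is a leftover. Even if such a role exists, section 6.9 should state it and give the Sponsor a deadline.

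On severity, a reader might infer that deaths or life-threatening events would go undetected. They would not: section 6.3 captures them as serious outcomes and section 6.9 has fields for fatal cases. The gap is in grading and tabulation. Nor is section 7 an automatic trigger at CTCAE grade 2. It concerns infection judged unsuitable for continued treatment, and withdrawal is at the investigator's discretion. It shows only that the protocol relies on CTCAE grades outside section 6.2.

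On causality, a reader might infer that section 6.7 conflicts with some other scale. It does not, since the supplied text contains only one. A reader might also infer that drug-related events will be under-counted. The plan defines no drug-related count and no cut-off, so that does not follow as it stands. SAE reporting is required whatever the relationship, so the wording cannot block an SAE report, and the same scale applies to both blinded arms.

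**Conclusion.** The concern holds in three parts of unequal weight.

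- **Routing: must be fixed.** Section 6.9 names two recipients and attaches the protocol's only SAE deadline to the one with no stated role. It applies to every SAE. Section 6.1 reports no severe adverse reactions in the completed studies, so SAEs may be few, but each would meet this rule. The conclusion assumes that the removed pages do not define the company's role; if they do, the missing Sponsor deadline remains.
- **Severity: a real conflict, for the same amendment.** Two numbered scales coexist without a mapping, and the one in section 6.6 cannot grade life-threatening or fatal events. It applies to the grading of every AE. It rests on the protocol text alone, not on the content of CTCAE.
- **Causality: secondary.** The definitions within one scale overlap at *Possible* and *Probable*, and push well-timed events with a plausible other cause down to *Unlikely*. Related events would be under-counted only if *Possible* and above were taken as related and *Unlikely* as not, a rule that the plan does not state. The documents give no basis for estimating how many events this would move.

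**What to change.** 1. **Section 6.9.** Attach the 48-hour deadline to the Sponsor (PRIG) and merge the two sentences into one rule. Delete the other company, or, if it holds a delegated safety function, state that function and keep the deadline to PRIG explicit.
2. **Sections 6.2, 6.6 and 9.2.4.2.** Use one severity scale for all AE grading and tabulation: CTCAE 4.0, as already named in section 6.2 and relied on in section 7. Remove the three-grade scale from section 6.6 and from the CRF, and name the tabulated scale in the analysis section.
3. **Section 6.7.** Reword *Possible* so that it covers reasonable timing where another cause could also explain the event, leaving *Probable* for events without a reasonable alternative. State in section 9.2.4.2 which categories count as related; *Possible*, *Probable* and *Definite* would be a natural choice.

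The cost is protocol and CRF wording, with site instruction and IRB approval of the amendment under section 10.5. Sample size and visits do not change. The number of events classed as *Possible* may rise somewhat, in both arms.

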7. DROPOUT, WITHDRAWAL, AND TERMINATION

If a subject's participation is terminated prematurely, the cause for the early termination will be documented.

Subjects will be free to drop out or withdraw at any time, for any reason, or they may be dismissed, if necessary, to protect their health or the integrity of the study.

Subjects who experience worsening of their skin condition will be evaluated for continued participation in the study based on the potential impact of the TC Cream on the integrity of the study results and the current FDA guidelines. The evaluation will take place as soon as possible after the episode(s) occurred.

Subjects who have a medical event equivalent to CTCAE grade 2 or higher infection that is deemed not suitable for continuation of the treatment may be considered to withdraw from the trial (as determined by the investigator).

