3.4.5 Early Withdrawal of Subjects

In the absence of treatment delays due to adverse events, treatment may continue until one of the following criteria applies:

- Voluntary patient withdrawal
- The investigator's decision that it is in the patient's best interest to withdraw
- If the patient becomes pregnant

Protocol Version: 00

- Noncompliance
- Significant protocol violation
- Safety reasons if any of the following occur:
 - Disease progression
 - Intercurrent illness that prevents further administration of treatment
 - Unacceptable adverse events(s)
 - Patient decides to withdraw from the study, or
 - General or specific changes in the patient's condition render the patient unacceptable for further treatment in the investigator's judgment.
- For any reason, at the Sponsor's or Investigators' discretion

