9.2 Data Analysis Considerations

9.2.1 Efficacy Analysis Populations

The populations include all patients who were randomized and received at least one dose of any study drug.

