9.2.3 Analysis Data Sets

- A. Intention-to-treat (ITT) Analysis should be defined as all subjects randomized and dispensed medication. Subjects should not be excluded from the ITT population for dropping out or failing to follow the protocol.
- B. Safety Analysis Sets are performed for all patients who underwent randomization and received at least 1 dose of study medication. So, with or without a test record, patients who experience adverse events should be included in the statistical analysis if they have received at least one dose of the study medication.

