9.2.4 Analysis Plan

The response to treatment with TC Cream will be assessed using an intention-to-treat (ITT) comparison with the placebo group (ratio of efficacy goals achieved).

The statistical analysis will be performed using a two-sided t-test with a 95% confidence interval (CI) for the difference in response rates between the two treatment groups (ITT, TC vs. Vehicle). A P value < 0.05 is considered to be statistically significant.

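### Participation can end for outcome-related reasons, and the plan gives patients without a final score no outcome value, so the primary response comparison is undefined for them

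*Combined protocol and SAP*

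**What the plan says.** **Ending participation.** Section 7 says that patients whose skin worsens "will be evaluated for continued participation in the study based on the potential impact of the TC Cream on the integrity of the study results"; the sentence then adds current FDA guidance as a second consideration. The same section says of subjects generally that "they may be dismissed, if necessary, to protect their health or the integrity of the study". Section 3.4.5 lists "Disease progression" among safety reasons, and closes with "For any reason, at the Sponsor's or Investigators' discretion". No threshold is given for any of these. Section 3.4.5 is headed as withdrawal of subjects, but its opening sentence is about how long treatment may continue.

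**Who is analysed.** Section 9.2.3: "Intention-to-treat (ITT) Analysis should be defined as all subjects randomized and dispensed medication", and "Subjects should not be excluded from the ITT population for dropping out or failing to follow the protocol". Section 9.2.1 defines the efficacy set differently: "The populations include all patients who were randomized and received at least one dose of any study drug".

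**What is compared.** Section 9.2.4: "The response to treatment with TC Cream will be assessed using an intention-to-treat (ITT) comparison with the placebo group (ratio of efficacy goals achieved"), by a two-sided t-test with a 95% confidence interval for the difference in response rates.

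**Missing outcomes.** Section 8.1 asks that missing CRF data be explained. The only scoring rule for missing values concerns unanswered PDI items (Section 5.1.4). Nothing readable covers a missing ISGA, target-lesion or PASI result, and no sensitivity analysis is planned.

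**The concern.** ISGA success in Section 5.1.1 is a fall of two or more grades from baseline. A patient who is worse than at baseline cannot meet it at that visit. A rule that reviews the participation of worsening patients therefore acts mostly on likely failures, and one of its stated grounds is the effect on the results.

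That would matter less if the plan fixed what happens to these patients in the analysis. It fixes only that they belong to the ITT population. A patient can be in the population and have no value to analyse. Unless missing responses are coded beforehand, a t-test on response will normally leave them out. An analysis labelled ITT would then describe only patients with a final score, and the choice could be made after the data exist. With 44 patients per arm, a few such patients can move the result across the 0.05 threshold.

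**Working it through.** **The plan's own figure.** Section 9.1 gives 44 per arm with 90% one-sided power, but no response rates, effect size or dropout rate, so 88 cannot be reproduced. Solving backwards at alpha 0.05 without continuity correction, vehicle rates of 5% to 40% imply a detectable difference of about 23 to 31 points one-sided, or 26 to 34 points two-sided. Distortions of several points should be read against that scale.

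**Do the sections settle the outcome of a withdrawn patient?**
- Section 9.2.3 settles membership of the analysis set, not the value.
- Section 5.1.1 defines ISGA success on an unspecified follow-up score, Section 5.1.2 scores target lesions at the end of treatment, and Section 5.1.3 takes PASI 75 at the end of 8 weeks.
- For a patient withdrawn at Week 4, at least three readings are open: non-responder, last available score, or left out. Only the third conflicts with Section 9.2.3.

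**Size if withdrawn patients are left out, by rates.** All rates here are assumptions. Let p be the true response rate and d the proportion withdrawn, all withdrawals being failures. The observed-case rate is p/(1 − d).
- True rates 40% and 15%, difference 25 points.
- 20% TC and 5% vehicle withdrawn: 0.40/0.80 − 0.15/0.95 = 0.500 − 0.158 = 34.2 points.
- 5% TC and 20% vehicle withdrawn: 0.40/0.95 − 0.15/0.80 = 0.421 − 0.188 = 23.4 points.
- 5% withdrawn in each arm: 0.421 − 0.158 = 26.3 points.
- No true effect, 20% in both arms, 25% and 5% withdrawn: 0.20/0.75 − 0.20/0.95 = 0.267 − 0.211 = 5.6 points.
- No true effect, 10% and 5% withdrawn: 0.20/0.90 − 0.20/0.95 = 0.222 − 0.211 = 1.2 points.

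**Size by counts at 44 per arm.** Assume 15 responders on TC and 7 on vehicle, all removed patients being non-responders. P-values are from a pooled two-proportion z-test, used here as an approximation to the planned test.
- Counted as failures, whatever the removals: 15/44 − 7/44 = 34.1% − 15.9% = 18.2 points, p = 0.049.
- Left out, 4 removed per arm: 15/40 − 7/40 = 37.5% − 17.5% = 20.0 points, p = 0.045.
- Left out, 9 TC and 2 vehicle removed: 15/35 − 7/42 = 42.9% − 16.7% = 26.2 points, p = 0.011.
- Left out, 2 TC and 9 vehicle removed: 15/42 − 7/35 = 35.7% − 20.0% = 15.7 points, p = 0.13.

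**The case against.** A reader might infer that the plan amounts to a biased completer analysis. The documents do not support that. Section 9.2.3 forbids excluding dropouts, Section 9.2.4 makes the comparison ITT, and a binary response can be coded as failure for all 44 patients in each arm. A non-responder reading is as open as an observed-case one. This stands, and it limits the point to an outcome that is undefined.

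Other objections, and what remains of them:
- **Evaluation is not removal.** Section 7 says worsening patients are evaluated for continuation and names FDA guidance too. Section 3.4.5 is partly about stopping treatment, which need not mean losing data. Both are fair, but study results remain a stated ground, and the two sections do not separate stopping the cream from leaving the study.
- **A visit after withdrawal may exist.** The Schedule of Events (Section 4.1) is not readable, so an early-termination visit cannot be ruled out. Such a visit alone would supply neither a Week 8 score nor an analysis rule.
- **Blinding.** Section 3.2 blinds subjects, investigators and the monitor, which constrains deliberate selection by arm. It does not prevent unequal losses when the arms worsen at different rates.
- **Likely direction.** If the cream works and worsening drives removal, vehicle should lose more patients, and the difference would be slightly understated (23 against 25 points). This is a fair reason not to presume bias in favour of TC. Other withdrawal reasons in Section 3.4.5, such as adverse events or noncompliance, could act the other way.
- **Two efficacy sets.** The mismatch between Sections 9.2.1 and 9.2.3 is a separate inconsistency. It is not shown to cause the bias described here.

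**Conclusion.** The point holds in this form: participation can end for outcome-related reasons, including a ground tied to the study results, and the plan assigns no outcome to a patient who then lacks a final score. The primary comparison is undefined for such patients and could become observed-case by default, contrary to Section 9.2.3.

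The documents support neither a claim that bias is certain nor a claim that it favours TC. Under the assumed 40% and 15%, with every withdrawal a failure, the difference moves from 25 points to 34 or 23 according to which arm loses more. With small and equal losses the change is about one point. In the count example the same patients give p-values from 0.011 to 0.13 according to handling and imbalance. These rates and removal counts are illustrations, since the protocol states none. That an open analysis choice can decide significance at this sample size is reason enough to close it before unblinded data are seen.

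**What to change.** 1. **Sections 7 and 3.4.5.** Delete the two integrity grounds in Section 7 as reasons for ending follow-up or data collection. Decisions to stop the cream are unchanged. The two sections must be reconciled on how worsening is handled, and on stopping treatment as distinct from leaving the study.
2. **Follow-up.** Patients who stop the cream and still consent stay on the existing visit schedule and are scored at Week 8.
3. **Section 9.2.4.** Name Week 8 as the time point for the response endpoints. Analyse all randomized patients as randomized, and count anyone without a Week 8 score as a non-responder. Add one simple sensitivity analysis, for example with the last available score after baseline. Multiple imputation or a tipping-point analysis is optional.
4. **Sections 9.2.1 and 9.2.3.** Use that single efficacy set in both places.

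Step 2 matters as much as step 3. Counting missing patients as failures recovers the 25 points in the illustration only because every withdrawal was assumed to be a failure. Where some would have responded, it understates the rate in that arm, so few Week 8 scores should be missing.

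The cost is protocol wording, a few retained visits, and somewhat lower reported response rates in any arm with withdrawals. No additional patients are needed to make these changes.
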